7. DISCONTINUATION OF STUDY INTERVENTION AND PARTICIPANT DISCONTINUATION/WITHDRAWAL

7.1. Discontinuation of Study Intervention

It may be necessary for a participant to permanently discontinue study intervention. Reasons for permanent discontinuation of study intervention include the following: AEs; parent(s)/legal guardian or participant request; investigator request; pregnancy; and protocol deviation (including no longer meeting all inclusion criteria or meeting 1 or more exclusion criteria).

Note that discontinuation of study intervention does not represent withdrawal from the study. If study intervention is permanently discontinued, the participant should remain in the study to be evaluated for safety. All participants for whom study intervention was discontinued after the last dose of the primary series or the booster dose will be followed for safety and immunogenicity, as applicable. See the [SoA](#) for data to be collected at the time of discontinuation of study intervention and follow-up for any further evaluations that need to be completed.

In the event of discontinuation of study intervention, it must be documented on the appropriate CRF/in the medical records whether the participant is discontinuing further receipt of study intervention or also from study procedures, postvaccination study follow-up, and/or future collection of additional information.

7.2. Participant Discontinuation/Withdrawal From the Study

A participant may withdraw from the study at any time at their own request. Reasons for discontinuation from the study include the following: refused further study procedures; lost to follow-up; death; study terminated by sponsor; AEs; pregnancy; parent(s)/legal guardian or participant request; medication error without an associated AE; no longer meets eligibility criteria; protocol deviation; other.

If a participant does not return for a scheduled visit, every effort should be made to contact the participant or participant's parent(s)/legal guardian. All attempts to contact the participant or participant's parent(s)/legal guardian and information received during contact attempts must be documented in the participant's source document. In any circumstance, every effort should be made to document participant outcome, if possible.

The investigator or his or her designee should capture the reason for withdrawal in the CRF for all participants.

If a participant is withdrawn, the investigator should request that the participant return for 1 final visit to perform the safety-related procedures indicated for the next study scheduled visit. Any AEs or SAEs that are continuing at the time of withdrawal from the study should be followed until resolution or, in case of permanent impairment, until the condition stabilizes.

A final unplanned telephone contact visit ~6 months after the last vaccination preceding withdrawal for the collection of safety information, unless consent for further contact has been withdrawn or the participant is lost to follow-up, should be performed.

If the participant withdraws from the study and also withdraws consent (see [Section 7.2.1](#)) for disclosure of future information, no further evaluations will be performed and no additional data will be collected. The sponsor may retain and continue to use any data collected before such withdrawal of consent.

7.2.1. Withdrawal of Consent

Participants who request (or whose parent(s)/legal guardian request) to discontinue receipt of study intervention will remain in the study and must continue to be followed for protocol-specified follow-up procedures. The only exception to this is when a participant or participant's parent(s)/legal guardian specifically withdraws consent for any further contact with them or persons previously authorized by the participant to provide this information. Participants or participants' parent(s)/legal guardian should notify the investigator in writing of the decision to withdraw consent from future follow-up, whenever possible. The withdrawal of consent should be explained in detail in the medical records by the investigator, as to whether the withdrawal is only from further receipt of study intervention or also from study procedures and/or postvaccination study follow-up, and entered on the appropriate CRF page. In the event that vital status (whether the participant is alive or dead) is being measured, publicly available information should be used to determine vital status only as appropriately directed in accordance with local law.

7.3. Lost to Follow-Up

A participant will be considered lost to follow-up if the participant repeatedly fails to return for scheduled visits and he or she, or the participant's parent(s)/legal guardian, is unable to be contacted by the study site.

The following actions must be taken if a participant fails to attend a required study visit:

- The site must attempt to contact the participant or the participant's parent(s)/legal guardian and reschedule the missed visit as soon as possible. Counsel the participant or the participant's parent(s)/legal guardian on the importance of maintaining the assigned visit schedule, and ascertain whether the participant wishes to and/or should continue in the study;
- Before a participant is deemed lost to follow-up, the investigator or designee must make every effort to regain contact with the participant or the participant's parent(s)/legal guardian (where possible, 3 telephone calls and, if necessary, a certified letter to the participant's last known mailing address or local equivalent methods). These contact attempts should be documented in the participant's medical record;
- Should the participant or the participant's parent(s)/legal guardian continue to be unreachable, the participant will be considered to have withdrawn from the study.

8. STUDY ASSESSMENTS AND PROCEDURES

8.1. Administrative Procedures

The investigator (or an appropriate delegate at the investigator site) must obtain a signed and dated ICD and assent (where appropriate) before performing any study-specific procedures.

The date of birth will be collected to critically evaluate the safety profile by age.

Study procedures and their timing are summarized in the [SoA](#). Protocol waivers or exemptions are not allowed.

Adherence to the study design requirements, including those specified in the [SoA](#), is essential and required for study conduct.

All screening evaluations must be completed and reviewed to confirm that potential participants meet all eligibility criteria. The investigator will maintain a screening log to record details of all participants screened and to confirm eligibility or record reasons for screening failure, as applicable.

Every effort should be made to ensure that protocol-required tests and procedures are completed as described. However, it is anticipated that from time to time there may be circumstances outside the control of the investigator that make it unfeasible to perform the test. In these cases, the investigator must take all steps necessary to ensure the safety and well-being of the participant. When a protocol-required test cannot be performed, the investigator will document the reason for the missed test and any corrective and preventive actions that they have taken to ensure that required processes are adhered to as soon as possible. The study team must be informed of these incidents in a timely manner.

8.1.1. Mobile Visits

Mobile visits may take place as approved by the sponsor.

In the event that an in-person visit is not feasible at the site, the following may be performed by a licensed healthcare professional at an alternate site approved by the investigator (see the [SoA](#)):

- All study activities.

8.2. Efficacy and/or Immunogenicity Assessments

This study does not include immunogenicity or efficacy assessments.

8.3. Safety Assessments

Planned time points for all safety assessments are provided in the [SoA](#). Unscheduled safety measurements may be obtained at any time during the study to assess any perceived safety issues.

A clinical assessment, including medical history, will be performed on all participants at their first visit to establish a baseline. Significant medical history will be documented in the CRF.

AEs and SAEs are collected, recorded, and reported as defined in [Section 8.4](#).

Acute reactions within the first 30 minutes after administration of the study intervention will be assessed and documented in the AE CRF.

The safety parameters also include reactogenicity e-diary reports of local reactions, systemic events (including fever), and use of antipyretic medication that occur in the 7 days after administration of the study intervention. These prospectively self-collected occurrences of local reactions and systemic events are graded as described in [Section 8.3.3.1](#).

8.3.1. Clinical Assessments and Physical Examinations

A clinical assessment, including medical history, will be performed on all participants prior to the first vaccination to determine participant eligibility and to establish a clinical baseline. Significant medical history and significant findings from any PE (if needed to comprehensively evaluate the participant) will be recorded as medical history in the CRF.

PE findings collected during the study will be considered source data and will not be required to be reported, unless otherwise noted. Any untoward PE findings that are identified during the active collection period and meet the definition of an AE or SAE ([Appendix 3](#)) must be reported according to the processes in [Sections 8.4.1 to 8.4.3](#).

8.3.2. Vital Signs

Prevaccination temperature will be measured as per usual clinical practice.

Any untoward vital sign findings that are identified during the active collection period and meet the definition of an AE or SAE ([Appendix 3](#)) must be reported according to the processes in [Sections 8.4.1 to 8.4.3](#).

8.3.3. Electronic Diary

All participants will report prompted local and systemic events in an e-diary to assess reactogenicity. The participant's parent(s)/legal guardian will be asked to monitor and record local reactions, systemic events, including fever, and antipyretic/pain medication used to treat symptoms, each evening for 7 days following vaccination (Day 1 through Day 7, where Day 1 is the day of vaccination) on a system that uses a PDA or other technology. This system, hereafter referred to as the participant's e-diary, allows recording of these assessments only within a fixed time window, thus providing the accurate representation of the participant's experience at that time. Data on local reactions, systemic events, and antipyretic/pain medication used to treat symptoms reported in the e-diary will be transferred electronically to the e-diary vendor, where they will be available for review by investigators, their qualified designees, and sponsor staff at all times via an internet-based portal. At intervals agreed to by the vendor and Pfizer, these data will be transferred electronically to Pfizer for analysis and reporting. These data do not need to be reported by the investigator in the CRF. However, if a participant withdraws because of prompted reactogenicity events reported in the e-diary, the event(s) should be recorded on the AE page of the CRF, regardless of whether the investigator considers the event(s) to be clinically significant.

Investigators (or an appropriately qualified designee) are required to review the e-diary data online to evaluate participant compliance and as part of the ongoing safety review.

The investigator or designee must contact the participant's parent(s)/legal guardian in order to obtain stop dates for any reactions ongoing on the last day that the e-diary was completed. The stop dates should be documented in the source documents and the information entered in the CRF.

8.3.3.1. Grading Scales

The grading scales used in this study to assess AEs as described below are based on concepts outlined in the FDA CBER guidelines on toxicity grading scales for healthy adult and adolescent volunteers enrolled in preventive vaccine clinical trials, with adaptations for applicability to healthy younger children.⁹

8.3.3.2. Local Reactions

From Day 1 through Day 7, where Day 1 is the day of vaccination, participants' parent(s)/legal guardian(s) will be asked to assess redness, swelling, and pain at the participant's injection site and to record the findings in the e-diary in the evening. For participants <12 years of age, redness and swelling will be measured and recorded in caliper units (range: 1 to 14) and then categorized during analysis as mild, moderate, or severe based on the grading scale in Table 1. For participants ≥12 years of age, redness and swelling will be measured and recorded in caliper units (range: 1 to 21) and then categorized during analysis as mild, moderate, or severe based on the grading scale in Table 2. Caliper units can be converted to centimeters according to the following scale: 1 caliper unit = 0.5 cm. Pain at the vaccine injection site will be assessed by the participant's parent(s)/legal guardian as mild, moderate, or severe according to the grading scale in Table 1 or Table 2. The parent(s)/legal guardian of a participant with severe (Grade 3 or above) redness or swelling will be prompted to contact the investigator to perform an unscheduled visit and assess the reaction.

Only an investigator is able to classify a participant's local reaction as Grade 4, after PE of the participant or documentation from another medically qualified source (eg, emergency room or hospital record) or, in the case of pain at the injection site only, telephone contact with the participant's parent(s)/legal guardian. If a participant experiences a Grade 4 local reaction, the investigator must immediately notify the sponsor. Site staff will educate the participant's parent(s)/legal guardian regarding signs and symptoms that would prompt site contact. The procedure for notification of the sponsor is provided in the study documentation.

If a local reaction persists beyond the end of the e-diary period following vaccination, the participant's parent(s)/legal guardian will be requested to report that information and/or any new AEs that develop to the investigator. The investigator will enter this additional information in the CRF.

Table 1. Local Reaction Grading Scale – Participants ≥ 5 to <12 Years of Age

	Grade 1 Mild	Grade 2 Moderate	Grade 3^a Severe	Grade 4^b
Redness	0.5 cm to 2.0 cm (1 to 4 caliper units)	>2.0 cm to 7.0 cm (5 to 14 caliper units)	>7 cm (>14 caliper units)	Necrosis or exfoliative dermatitis
Swelling	0.5 cm to 2.0 cm (1 to 4 caliper units)	>2.0 cm to 7.0 cm (5 to 14 caliper units)	>7 cm (>14 caliper units)	Necrosis
Pain at injection site (tenderness)	Does not interfere with activity	Interferes with activity	Prevents daily activity ^c	Emergency room visit or hospitalization for severe pain (tenderness) at the injection site

- Participants experiencing \geq Grade 3 local reactions may be seen by the study site. Refer to the Unscheduled Visits section (Section 8.11) for further guidance.
- Grade 4 assessment should be made by an investigator; Grade 4 will not be collected in the diary but will be collected in the case report form.
- Prevents daily activity, ie, results in missed days of school or is otherwise incapacitating, or includes use of narcotics for analgesia.

Table 2. Local Reaction Grading Scale – Participants ≥ 12 Years of Age

	Grade 1 Mild	Grade 2 Moderate	Grade 3^a Severe	Grade 4^b
Redness	>2.0 cm to 5.0 cm (5 to 10 caliper units)	>5.0 to 10 cm (11 to 20 caliper units)	>10 cm (>20 caliper units)	Necrosis or exfoliative dermatitis
Swelling	>2.0 cm to 5.0 cm (5 to 10 caliper units)	>5.0 cm to 10.0 cm (11 to 20 caliper units)	>10 cm (>20 caliper units)	Necrosis
Pain at injection site	Does not interfere with activity	Interferes with activity	Prevents daily activity ^c	Emergency room visit or hospitalization for severe pain at the injection site

- Participants experiencing \geq Grade 3 local reactions may be seen by the study site. Refer to the Unscheduled Visits section (Section 8.11) for further guidance.
- Grade 4 assessment should be made by an investigator; Grade 4 will not be collected in the diary but will be collected in the case report form.
- Prevents daily activity, ie, results in missed days of work or school or is otherwise incapacitating, or includes use of narcotics for analgesia.

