8.10.8. Visit 8 – Month 24 Telephone Call (172-192 Days After Visit 6)

- Record AEs/NDCMCs/SAEs as described in [Section 8.4](#).
- Record nonstudy vaccinations and medications as described in [Section 6.9](#).
- Complete the source documents.
- The investigator or an authorized designee completes the CRFs.
- Inform the participant or participant's parent(s)/legal guardian that the participant's study participation has ended.

8.11. Unscheduled Visit for Fever or a Grade 3 or Suspected Grade 4 Reaction

If redness or swelling >14 caliper units for participants 5 through 11 years of age or >20 caliper units for participants ≥12 years of age ([Section 8.3.3.2](#)), severe headache, severe joint pain ([Section 8.3.3.3](#)), or fever (≥102.1°F [≥39.0°C]) ([Section 8.3.3.4](#)) is reported by the participant's parent(s)/legal guardian in the reactogenicity e-diary, a telephone contact should occur to ascertain further details and determine whether a site visit is clinically indicated.

If a suspected Grade 4 local reaction ([Section 8.3.3.2](#)), Grade 4 systemic event ([Section 8.3.3.3](#)), or fever ($>104.0^{\circ}\text{F}$ [$>40.0^{\circ}\text{C}$]) ([Section 8.3.3.4](#)) is reported by the participant's parent(s)/legal guardian in the reactogenicity e-diary, a telephone contact or site visit should occur to confirm the fever and determine whether the event meets the criteria for Grade 4.

A site visit must be scheduled as soon as possible to assess the participant unless any of the following is true:

- The participant is unable to attend the unscheduled visit.
- The local reaction/systemic event is no longer present at the time of the telephone contact.
- The participant's parent(s)/legal guardian recorded an incorrect value in the e-diary (confirmation of an e-diary data entry error).
- The PI or authorized designee determined it was not needed.

This telephone contact will be recorded in the participant's source documentation and the CRF.

If the participant is unable to attend the unscheduled visit, or the PI or authorized designee determined it was not needed, any ongoing local reactions/systemic events must be assessed at the next study visit.

During the unscheduled visit, the reactions/events should be assessed by the investigator or a medically qualified member of the study staff, such as a study physician or a study nurse, as applicable to the investigator's local practice, who will:

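### The under-12 e-diary range stated for redness and swelling (1 to 14 caliper units) contains no Grade 3 value and contradicts Protocol Table 1, Protocol Section 8.11 and SAP Table 5

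*Protocol*

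**What the plan says.** Protocol Section 8.3.3.2 sets the recording range for the younger group: "For participants <12 years of age, redness and swelling will be measured and recorded in caliper units (range: 1 to 14"). The recorded values are not graded at entry; they are kept as units "and then categorized during analysis as mild, moderate, or severe based on the grading scale in Table 1". The conversion is "1 caliper unit = 0.5 cm".

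Table 1, which applies from 5 to under 12 years, gives Grade 2 as ">2.0 cm to 7.0 cm (5 to 14 caliper units") and Grade 3 as ">7 cm (>14 caliper units"). For the older group the text reads "For participants ≥12 years of age, redness and swelling will be measured and recorded in caliper units (range: 1 to 21"), and Table 2 starts Grade 3 above 20 units.

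Three other places rely on values above 14 units in the younger group:

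- Section 8.3.3.2 says that parents of a child with Grade 3 redness or swelling will be prompted to contact the investigator.
- Section 8.11 begins "If redness or swelling >14 caliper units for participants 5 through 11 years of age" and calls for a telephone contact when this is reported in the e-diary.
- SAP Table 5 (Section 3.1.1.1.2) assigns Grade 3 to e-diary values above 14 units, or to a severe grade on the AE CRF.

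Where the e-diary and the AE CRF both report the event, SAP Section 3.1.1 takes the higher grade.

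**The concern.** The older group's range extends one unit past its Grade 3 boundary. The younger group's range stops exactly on its boundary. Because grading is done later from the stored number, the range itself decides which grades the e-diary can produce. Under the range as written, the e-diary cannot produce Grade 3 redness or swelling in a child under 12.

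Local reactions by maximum severity are a primary safety summary, presented separately for each age group (Protocol Section 9.3.2, SAP Section 6.1.1.1). If the diary was capped, a very low rate of severe redness and swelling in the younger group could be an artefact of the recording scale, and nothing in the planned tables would reveal it. The e-diary condition in Section 8.11 would also be one that no diary entry could meet.

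**Working it through.** **Inputs.** Conversion of 0.5 cm per unit, stated ranges, and grade boundaries: Protocol Section 8.3.3.2, Tables 1 and 2.

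**Step 1: reproduce the plan's cut-offs.** Length in cm = units × 0.5.

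- Under 12, top of Grade 2: 14 × 0.5 = 7.0 cm, which matches Table 1.
- 12 and over, top of Grade 2: 20 × 0.5 = 10.0 cm, which matches Table 2.

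The thresholds are therefore consistent in both units. The fault lies in the stated range, not in the grade table.

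**Step 2: assign every whole unit in each stated range to a grade.**

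| Age group | Stated range | Below Grade 1 | Grade 1 | Grade 2 | Grade 3 |
|---|---|---|---|---|---|
| Under 12 | 1 to 14 | none | 1–4 (0.5–2.0 cm) | 5–14 (2.5–7.0 cm) | none: 0 of 14 values |
| 12 and over | 1 to 21 | 1–4 (0.5–2.0 cm) | 5–10 (2.5–5.0 cm) | 11–20 (5.5–10.0 cm) | 21 (10.5 cm): 1 of 21 values |

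Allowing fractions of a unit would not change the first row, since nothing up to 14 exceeds 14.

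**Step 3: test one more unit.** With a range of 1 to 15, the value 15 is 15 × 0.5 = 7.5 cm and falls in Grade 3, just as 21 does for the older group.

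**Step 4: follow a reaction over 7 cm under a capped diary.** The largest admissible entry is 14, which Table 1 grades as moderate. The remaining routes are these:

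- *AE CRF.* SAP Table 5 accepts a severe grade from it, and the higher of the two sources is used. However, SAP Section 3.1.1 states that the AE CRF does not hold the measured size, and Protocol Section 10.3.4 defines CRF severity by interference with usual function. A wide but untroubling redness could properly be entered as mild, and the higher of the two grades would remain Grade 2. Protocol Section 8.3.3 also says that e-diary data need not be entered in the CRF.
- *Measurements in query responses.* SAP Section 3.1.1 would use them, but discusses them in connection with missing e-diary entries. An entry of 14 is not missing.
- *Unscheduled visit.* Section 8.11 has the site measure diameters and complete a CRF page. The SAP names only the e-diary and the AE CRF as reactogenicity sources and gives no rule for using measurements from that page.

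**Step 5: bound the exposed group.** This counts participants on the scale, not misgraded children. The minimum stratum is 600, so 600 × 3/4 = 450 on VLA15. The maximum is 3000 − 600 = 2400 (1800 on VLA15) under the protocol total, or 3550 − 600 = 2950 (about 2210 on VLA15) under the total in SAP Section 2.3. Each participant has up to four doses. SAP Section 3.1.1.1.2 grades by age at each dose, so children who turn 12 move to the other scale. The documents give no rate of reactions over 7 cm, so no number affected can be derived.

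**The case against.** The strongest reply is that a single parenthesis conflicts with everything around it. Table 1 has a category above 14 units, the same section prompts parents of children with severe reactions, and Section 8.11 and SAP Table 5 both treat more than 14 units as an e-diary value. The e-diary build is not in the documents, so a misprinted range with a correctly built diary fits them as well as a capped diary does. The measuring tool may be a tape measure and need not stop at 14 units. This stands: the consequence is conditional on the build.

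A reader might infer that severe redness or swelling cannot be recorded at all in children under 12, or that its rate must be about zero by construction. The documents do not support that, because SAP Table 5 admits a severe AE CRF grade and the higher source is used. That route is weaker than the diary, since it carries no size and grades by function, but it exists.

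A reader might also infer that safety follow-up is lost. That goes too far. At each of the four vaccination visits (Protocol Sections 8.10.1, 8.10.2, 8.10.3 and 8.10.6) parents of children aged 5 through 11 are told to contact the site for redness or swelling over 7 cm, whatever the diary holds. Only the trigger that depends on a diary value is in doubt. That instruction does not, however, correct the stored value from which the grade is derived.

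**Conclusion.** The inconsistency is certain. The stated under-12 range contains no Grade 3 value and cannot be reconciled with Table 1, Section 8.11 or SAP Table 5. It is more than clerical, because the recorded value determines the grade in a primary safety summary.

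The effect on results depends on one assumption that the documents do not settle: that the e-diary was programmed to the stated range. If it was, every diary-recorded reaction over 7 cm in a child under 12 at that dose is graded moderate from the e-diary, the diary-based trigger above 14 units cannot fire, and severe grades for redness and swelling reach the analysis only through the AE CRF. If it was not, the protocol sentence is wrong and the data are unaffected. The size of any misgrading is unknown.

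**What to change.** Confirm, from the e-diary specification, the range actually programmed for participants under 12 and whether the contact prompt responds to a value above 14. Then correct Protocol Section 8.3.3.2 so that such a value is recordable: for example 1 to 15, with 15 meaning more than 14 units, parallel to 1 to 21 for the older group. The grade thresholds stay as they are, and Sections 8.3.3.2 and 8.11 and SAP Table 5 should then agree.

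SAP version 3 is dated 01 Aug 2025 against a protocol of 25 Jul 2022, so some or all doses may already have been given. If data were collected with a cap at 14, report by vaccine group the number of participants with entries at 14 units, and state that the e-diary could not distinguish Grade 3 from Grade 2 for those doses.

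The cost is one corrected sentence and a configuration check, plus one added table row and a stated limitation if a cap existed. A capped build would need reprogramming for any doses still to come, and earlier doses could not be recovered from the diary.
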